3.1.1 Part A - Dose Escalation

In Part A, a 3 + 3 + 3 design will be used to assess the safety of relatlimab. The dose levels evaluated during dose escalation are provided in Table 3.1.1-1. Dose escalation rules are outlined below. Three subjects will initially be treated in each dose cohort; in Dose Cohort 1, the first 3 subjects will be designated as sentinel subjects and will begin treatment at least 5 days apart. Subjects in subsequent cohorts will not be required to observe the 5-day interval between treatment start dates.

Dose escalation will be based on the number of DLTs experienced during the DLT evaluation interval as determined by the Medical Monitor and Investigators (see [Section 3.1.3](#) for DLT criteria). The DLT evaluation interval begins on the first day of treatment and continues for 8 weeks, ie, through Day [REDACTED] of the first cycle. Subjects who receive at least 1 dose of study drug during the 8-week evaluation interval will be considered evaluable for DLT determination. In consultation with Investigators, the Sponsor has the option to investigate dose levels intermediate to those defined in the protocol.

Dose escalation in Part A (Table 3.1.1-1) will proceed as follows:

- If none of the first [REDACTED] evaluable subjects in a dose cohort experiences a DLT within the DLT evaluation interval, then the next [REDACTED] subjects will be treated at the next higher dose cohort.
- If 1 of the first [REDACTED] evaluable subjects in a cohort experiences a DLT within the DLT evaluation interval, then [REDACTED] additional subjects will be treated in that dose cohort.
 - If no more than [REDACTED] of the first [REDACTED] evaluable subjects experiences a DLT during the DLT evaluation interval, then the next [REDACTED] subjects will be enrolled at the next higher dose cohort.
 - If [REDACTED] of the first [REDACTED] evaluable subjects in a cohort experience a DLT, that cohort will be expanded to [REDACTED] evaluable subjects.
- If \geq [REDACTED] of the first [REDACTED] evaluable subjects, \geq [REDACTED] of the first [REDACTED] evaluable subjects, or \geq [REDACTED] of the first [REDACTED] evaluable subjects in a cohort experience a DLT within the DLT evaluation interval, that dose level will have exceeded the MTD and dose escalation will be terminated.

Table 3.1.1-1: Dose Escalation Schedule for Part A - Relatlimab Monotherapy

Dose Cohort Number	Relatlimab Dose (IV; mg)	Total Subjects
1	[REDACTED]	n = approximately [REDACTED]
2	[REDACTED]	n = approximately [REDACTED]
3	[REDACTED]	n = approximately [REDACTED]
4	[REDACTED]	n = approximately [REDACTED]
Total		N = approximately [REDACTED]

In consultation with Investigators, the Sponsor may investigate dose levels intermediate to those defined in the protocol. Prior to declaring the MTD (or MAD), and in consultation with

Investigators, the Sponsor has the option to expand any cohort previously established to be safe in order to obtain additional experience or to investigate dose levels intermediate to those defined in the protocol. Dose escalation rules (cohort size, DLT evaluation interval, cohort expansion criteria, etc.) will apply to the additional cohorts. A maximum of [REDACTED] subjects will be enrolled in any additional dose cohorts.

3.1.2 Part B - [REDACTED] mg Cohort Expansion

The purpose of this cohort expansion is to gather additional safety, tolerability, PK, and pharmacodynamic information regarding relatlimab dosed at [REDACTED] mg.

The dose selected for Part B has not exceeded the MTD in Part A (see rationale for dose selection in [Section 1.1.8.4](#)).

Four expansion cohorts will be restricted to the tumor types listed in [Figure 3.1-1](#) and Table 3.1.2-1. Continuous evaluation of toxicity events will be assessed throughout enrollment in the expansion cohorts. If, at any time, the aggregate rate of treatment-related toxicities meeting DLT criteria exceeds [REDACTED] across all subjects treated in Part B cohort expansions, the findings will be discussed with the Medical Monitor and Investigators; further enrollment may be interrupted. Depending on the nature and grade of the toxicity and after assessing the risk/benefit ratio, the dose for all or for select cohorts may be reduced.

Table 3.1.2-1: Tumor Types Eligible For Part B - Cohort Expansion Relatlimab Monotherapy

Tumor Type ^a	Total Subjects
Chronic Lymphocytic Leukemia (CLL)	n=approximately [REDACTED]
Diffuse Large B-Cell Lymphoma (DLBCL)	n=approximately [REDACTED]
Indolent non-Hodgkin Lymphoma (i-NHL)	n=approximately [REDACTED]
Hodgkin Lymphoma (HL)	n=approximately [REDACTED]
Total	n=approximately [REDACTED]

^a All subjects in Part B will be naive to immune cell-modulating antibody regimens (ICMARs), such as, but not limited to anti-CTLA-4, anti PD-L2, anti-KIR, and/or anti-OX40 antibodies except for anti-PD-1, anti-PD-L1, anti-CD137, anti-CD20, alemtuzumab, or anti-CD30 antibody therapy.

3.1.3 Part C - Dose Escalation Combination Therapy

As in Part A, a 3 + 3 + 3 design will also be used in Part C to assess the safety of relatlimab given in combination with nivolumab as a sequential infusion. A fourth subject may be enrolled at the beginning of a dose escalation cohort following agreement between the Investigator and the Sponsor/Medical Monitor, if subject is able to start the first day of dosing within approximately one week of the third subject in the same dose escalation cohort.

The dosages during dose escalation are provided in [Table 3.1.3-1](#).

Treatment in Part C will be initiated after the decision is made to escalate to the fourth dose cohort (■■■ mg anti-Lag-3 in combination with ■■■ mg anti-PD-1) in CA224020 study. At no point will the dose of relatlimab administered in combination with nivolumab (Part C) exceed doses of relatlimab that have been demonstrated previously to be safe on the monotherapy dose escalation arm (Part A). The escalation cohorts in Part C will be restricted to subjects with HL (naive to anti-PD-1/PD-L1 or whose disease progresses while-on or within 3 months of treatment with anti-PD-1 or anti-PD-L1 antibody) and DLBCL.

Dose escalation in Part C will proceed as described for Part A with the exception that the DLT observation period will be reduced from 8 weeks to 4 weeks. The rationale for the shorter observation period is presented in [Section 3.1.6.1](#). If no MTD is reached through Dose Cohort 3, then additional cohorts of relatlimab given in combination with nivolumab may be considered based on the aggregate safety experience during dose escalation. Enrollment of additional cohorts will be implemented upon consultation and agreement between Investigators and the Sponsor via a protocol amendment.

Prior to declaring the MTD (or MAD), and in consultation with Investigators, the Sponsor has the option to expand any cohort previously established to be safe in order to obtain additional experience or to investigate dose levels intermediate to those defined in the protocol. Dose escalation rules (cohort size, DLT evaluation interval, cohort expansion criteria, etc.) will apply to these expanded or additional cohorts. A maximum of ■ subjects will be enrolled in any additional or expanded dose cohorts.

After completion of the relatlimab (anti-LAG-3) ■■ mg and nivolumab ■■ mg cohort, the intermediate dose combination of anti-LAG-3 ■■ mg and nivolumab ■■ mg was investigated in Part C. The dose combination (■■■ mg anti-LAG-3/■■■ mg nivolumab) was well-tolerated in Part C and therefore selected for Part D (expansion).

No within-subject dose escalations will be permitted. If a dose level is found to exceed the MTD, subjects enrolled in that dose level may be reduced to a lower dose following consultation and agreement between Investigators and the Sponsor.

Table 3.1.3-1: Dose Escalation Schedule for Part C - Relatlimab in Combination with Nivolumab

Dose Cohort Number	Total Subjects	Relatlimab Dose (IV; mg)	Nivolumab Dose (IV; mg)
1	n = approximately ■■	■■■	■■■
2	n = approximately ■■	■■■	■■■
3	n = approximately ■■	■■■	■■■
Total	N = approximately ■■		

Note: Part C will be limited to subjects with HL (naive to anti-PD-1/PD-L1 or whose disease progresses while-on or within 3 months after treatment with anti-PD-1 or anti-PD-L1 antibody) and DLBCL.

3.1.4 Part D - Dose Expansion Combination Therapy

The purpose of cohort expansion is to gather additional safety, tolerability, preliminary efficacy, PK, and pharmacodynamic information in subjects treated with sequential infusion of nivolumab followed by administration of relatlimab. The doses selected for Part D will not exceed the MTD (or MAD if no MTD is determined) in Part C, but may incorporate assessment of other data including toxicities, PK, and pharmacodynamic data from Parts A, B and C and from the CA224020 study. The dose selected can be chosen while additional Part C dose escalation cohorts continue to be explored. Doses to be considered may include doses intermediate to those evaluated in Part C if recommended by the Investigators and the Sponsor. The intermediate dose of relatlimab (anti-lag-3) [REDACTED] mg and nivolumab [REDACTED] mg dose was well tolerated, and was thus selected for extension. Modeling may be used to help inform the selection of the combination dose level to carry forward in Part D if a dose below the MTD is chosen. Three expansion cohorts will be restricted to the tumor types listed in Table 3.1.4-1. Continuous evaluation of toxicity events will be assessed throughout enrollment in the expansion cohorts. If, at any time, the aggregate rate of treatment-related toxicities meeting DLT criteria exceeds [REDACTED] across all subjects treated in the Part D cohort expansions, the findings will be discussed with the Medical Monitor and Investigators; further enrollment may be interrupted. Depending on the nature and grade of the toxicity and after assessing the risk:benefit ratio, the dose for all or for select cohorts may be reduced. See [Section 8.1.3](#).

Table 3.1.4-1: Tumor Types Eligible For Part D - Cohort Expansion Relatlimab in Combination with Nivolumab

Tumor Type	Total Subjects
Hodgkin Lymphoma - anti-PD-1/PD-L1 naive	n=approximately [REDACTED]
Hodgkin Lymphoma - anti-PD-1/PD-L1 progressed	n=approximately [REDACTED]
Diffuse Large B-Cell Lymphoma	n=approximately [REDACTED]
Total	n=approximately [REDACTED]

3.1.5 Re-challenge in Dose Escalation (Part C) and Cohort Expansion (Part D)

If subjects progress during the clinical follow-up period or the survival follow-up period, they could further receive therapy with relatlimab alone or in combination therapy (Re-challenge) as long as the risk:benefit ratio is considered favorable by the Investigator and the Medical Monitor and the following eligibility criteria are met: 1) Subject has confirmed disease progression; 2) Subject has not experienced relatlimab related adverse events leading to permanent discontinuation. The original dose and schedule of therapy and protocol rules will apply. Thus subjects could receive therapy for up to [REDACTED] additional eight-week cycles. Subjects who are re-challenged and who subsequently have an objective response will not be included in the primary analysis of efficacy. Responses to re-challenge will be evaluated in a separate analysis. Subjects will not be re-challenged a second time.

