3.4.4 Treatment of Relatlimab or Nivolumab-Related Infusion Reactions

Since relatlimab and nivolumab contain only human immunoglobulin protein sequences, they are unlikely to be immunogenic and induce infusion or hypersensitivity reactions. However, if such a reaction were to occur, it might manifest with fever, chills, rigors, headache, rash, pruritus, arthralgias, hypotension, hypertension, bronchospasm, or other allergic-like reactions. All Grade 3 or 4 infusion reactions should be reported within 24 hours to the BMS Medical Monitor and reported as an SAE if it meets the criteria. Infusion reactions should be graded according to NCI CTCAE version 4.0 guidelines. If a subject has an infusion reaction with nivolumab, the relatlimab infusion can be given (without prophylactic medications) if the infusion reaction resolves within 3 hours. For scheduling purposes after a nivolumab infusion reaction, the relatlimab infusion may be given the next day. Prophylactic pre-infusion medications should be given prior to all subsequent nivolumab infusions.

Treatment recommendations are provided below and may be modified based on local treatment standards and guidelines, as appropriate:

For Grade 1 symptoms (Mild reaction; infusion interruption not indicated; intervention not indicated):

- Remain at bedside and monitor subject until recovery from symptoms. The following prophylactic premedications are recommended for future infusions: diphenhydramine 50 mg (or equivalent) and/or acetaminophen/paracetamol 325 to 1000 mg at least 30 minutes before additional study drug administrations.

For Grade 2 symptoms (Moderate reaction requires therapy or infusion interruption but responds promptly to symptomatic treatment [eg, antihistamines, non-steroidal anti-inflammatory drugs, narcotics, corticosteroids, bronchodilators, IV fluids]; prophylactic medications indicated for ≤ 24 hours).

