4 TREATMENTS

All protocol-specified investigational and non-investigational products are considered study drug.

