4.3.3 Criteria to Resume Treatment after Dose Delay

Subjects will be permitted to resume therapy at the same dose level(s) following resolution of the AE to \leq Grade 1 or to baseline within 6 weeks after last dose, with the exception of subjects who meet criteria for permanent discontinuation as specified in Section 4.3.5. Subjects who meet criteria for permanent discontinuation should receive no further study therapy. The following exceptions apply:

- If the toxicity resolves to \leq Grade 1 or baseline $>$ 6 weeks after last dose, but the subject does not otherwise meet the criteria for permanent discontinuation (see Section 4.3.5), and the Investigator believes that the subject is deriving clinical benefit, then the subject may be eligible to resume the study drug(s) following the approval of the BMS Medical Monitor.
- Subjects with a Grade 4 drug-related amylase and/or lipase increase that is not associated with symptoms or clinical manifestations of pancreatitis can be restarted on therapy once the levels have recovered to grade 3 or less, and after consultation with the BMS Medical Monitor.

- Subjects with baseline Grade 1 AST, ALT, or total bilirubin who require dose delays for reasons other than a drug-related hepatic event may resume treatment in the presence of Grade 2 AST, ALT, or total bilirubin.
- Subjects who require dose delays for drug-related elevations in AST, ALT, or total bilirubin may resume treatment when these values have returned to their baseline CTCAE Grade or normal and management with corticosteroids, if needed, is complete, provided the criteria for permanent discontinuation are not met.
- Subjects may resume treatment in the presence of Grade 2 fatigue.
- Subjects with drug-related endocrinopathies adequately controlled with only physiologic hormone replacement may resume treatment.
- Troponin elevations will require the participants to undergo a cardiac evaluation. Following this evaluation, determination of further treatment will be based on the discussion with the BMS Medical Monitor or designee.

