4.3.5 Guidelines for Permanent Discontinuation

Subjects meeting any of the following criteria will be required to permanently discontinue all study drug(s) (relatlimab in Part A and B; relatlimab and nivolumab in Parts C and D):

- Any Grade 3 non-skin, drug-related adverse event lasting > 7 days or recurs, with the following exceptions for laboratory abnormalities, drug-related uveitis, pneumonitis, bronchospasm, hypersensitivity reactions, infusion reactions, and endocrinopathies.
- Grade 3 drug-related myocarditis, uveitis, pneumonitis, bronchospasm, or hypersensitivity reaction of any duration.
- Grade 3 infusion reaction that does not return to Grade 1 in 6 hours or less.
- Any Grade 2 drug-related uveitis, eye pain or blurred vision that does not respond to topical therapy and does not improve to Grade 1 severity within the re-treatment period OR requires systemic treatment.
- Any Grade 4 drug-related AE or laboratory abnormality (including but not limited to creatinine, AST, ALT, or Total Bilirubin), except for the following events which do not require discontinuation:
 - Isolated Grade 4 electrolyte imbalances/abnormalities that are not associated with clinical sequelae and are corrected with supplementation/appropriate management within 72 hours of their onset.
 - Grade 4 neutropenia ≤ 7 days in duration.
 - Grade 4 lymphopenia or leukopenia.
 - Isolated Grade 4 lipase and/or amylase abnormalities that are not associated with symptoms or clinical manifestations of pancreatitis.
 - Isolated Grade 4 electrolyte imbalances/abnormalities that are not associated with clinical sequelae and are corrected with supplementation/appropriate management within 72 hours of their onset.
 - Grade 4 drug-related endocrinopathy adverse events, such as adrenal insufficiency, ACTH deficiency, hyper- or hypothyroidism, or glucose intolerance, which resolve or are adequately controlled with physiologic hormone replacement (corticosteroids, thyroid hormones) or glucose-controlling agents, respectively, may not require discontinuation after discussion with and approval from the BMS Medical Monitor.
- Grade 3 drug-related laboratory abnormalities do **not** require treatment discontinuation except:
 - Grade 3 drug-related thrombocytopenia > 7 days or associated with bleeding requires discontinuation.

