The consideration to re-initiate study therapy in selected cases at any time point after discontinuation could be made on a case-by-case basis after considering the overall benefit/risk profile and in consultation between the Investigator and the study Sponsor. The selected subjects will need to meet eligibility criteria. The original dose and schedule and protocol rules would apply accordingly.

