6 ADVERSE EVENTS

An *Adverse Event (AE)* is defined as any new untoward medical occurrence or worsening of a preexisting medical condition in a clinical investigation subject administered an investigational (medicinal) product and that does not necessarily have a causal relationship with this treatment. An AE can therefore be any unfavorable and unintended sign (such as an abnormal laboratory finding), symptom, or disease temporally associated with the use of investigational product, whether or not considered related to the investigational product.

The causal relationship to study drug is determined by a physician and should be used to assess all adverse events (AE). The causal relationship can be one of the following:

- Related: There is a reasonable causal relationship between study drug administration and the AE.
- Not related: There is not a reasonable causal relationship between study drug administration and the AE.

The term "reasonable causal relationship" means there is evidence to suggest a causal relationship.

Adverse events can be spontaneously reported or elicited during open-ended questioning, examination, or evaluation of a subject. Care should be taken not to introduce bias when collecting AE and/or SAEs. Inquiry about specific AEs should be guided by clinical judgement in the context of known adverse events, when appropriate for the program or protocol.

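### Re-challenge criterion 2 bars only relatlimab-related stops, so a resolved, non-life-threatening event attributed to nivolumab alone is no categorical bar to receiving both antibodies again

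*Combined protocol and SAP*

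**What the plan says.** Section 3.1.5 covers re-challenge in Parts C and D. A subject who progresses during clinical or survival follow-up may be treated again with relatlimab alone or with the combination, at the previous dose and schedule. The Investigator and Medical Monitor must consider the risk:benefit ratio favorable, and two specific criteria must be met. The first is confirmed progression. The second is "Subject has not experienced relatlimab related adverse events leading to permanent discontinuation". The synopsis words this criterion identically. Section 3.1 adds that the Section 3.3 eligibility criteria must be met.

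The stopping rule in Section 4.3.5 is not tied to one antibody. It withdraws all study drug, which it spells out as "relatlimab and nivolumab in Parts C and D". Its triggers include "Any Grade 3 non-skin, drug-related adverse event lasting > 7 days or recurs", with listed exceptions, and liver-test abnormalities that reach the DLT definition.

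Section 6 defines causality as "Related: There is a reasonable causal relationship between study drug administration and the AE", with Not related as the only alternative. Section 4 defines the term used there: "All protocol-specified investigational and non-investigational products are considered study drug".

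Two sentences deal with treatment after a stop. Section 4.3.3 says "Subjects who meet criteria for permanent discontinuation should receive no further study therapy". The closing paragraph of Section 4.3.5 says "The consideration to re-initiate study therapy in selected cases at any time point after discontinuation could be made on a case-by-case basis", subject to consultation with the sponsor and to eligibility.

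**The concern.** The rule that stops treatment does not ask which antibody caused the event. The one specific toxicity condition for giving both antibodies again does ask, and it counts only one of the two answers. The protocol gives no general method for attributing an event to a single antibody. It contemplates this only for infusion reactions, in Section 3.4.4: "If a subject has an infusion reaction with nivolumab, the relatlimab infusion can be given".

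Two sites could therefore handle the same event differently. One might treat any drug-related event on the combination as relatlimab-related and refuse re-challenge. The other might attribute it to nivolumab alone and find criterion 2 satisfied. At stake is re-exposure of a patient, at the same dose, to the regimen that had to be permanently stopped.

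**Working it through.** No arithmetic applies and the plan states no figure to reproduce. The check is to take one case through every rule that could stop it.

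**Case.** A Part D subject has Grade 3 colitis lasting more than 7 days, judged related to nivolumab and not to relatlimab. Both antibodies are permanently stopped under Section 4.3.5. The colitis resolves and the subject later progresses in follow-up.

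1. *Criterion 1, Section 3.1.5.* Progression is confirmed, so it is met.
2. *Criterion 2, Section 3.1.5.* The event is not judged relatlimab-related, so the criterion is met as worded. An event related to both antibodies would fail it, because the text does not say solely.
3. *Categorical exclusions in Section 3.3.2.* These cover life-threatening toxicity from earlier immune therapy unless unlikely to recur (2(o)), any history of myocarditis (2(h)(viii)), encephalitis, meningitis or uncontrolled seizures in the year before consent (2(h)(x)), and allergy to anti-PD-1 or anti-PD-L1 antibodies (3(a)). None is triggered. Events that do fall under them are already excluded and lie outside this point.
4. *Exclusion 2(b), autoimmune disease.* This is arguable. It covers active, known or suspected disease, and the protocol uses labels such as autoimmune hepatitis in Section 1.4.1.5. However, it exempts conditions that should not recur without an external trigger, so its application to a resolved drug-induced event is unclear.
5. *Exclusions 2(f) and 2(l).* 2(f) depends on the opinion of the Investigator or Sponsor that treatment would be hazardous. 2(l), other significant illness, does not clearly apply once the event has resolved.
6. *Sections 3.1.6 and 4.3.3.* Section 3.1.6 holds study drug for a DLT at any time and requires the Section 4.3.3 conditions before treatment restarts. Section 4.3.3 gives nothing further to a subject who meets the permanent-discontinuation criteria. Read literally, that would settle the case. But Section 4.3.5 also lists progression and completion of twelve cycles among those criteria. The literal reading would therefore rule out a subject who finished treatment and later progressed, an obvious candidate for re-challenge, and would make criterion 2 redundant. The closing paragraph of Section 4.3.5 then expressly allows re-initiation case by case.
7. *Risk:benefit judgment.* The Investigator and Medical Monitor must both find it favorable. This is a real safeguard, but a discretionary one.

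**Result.** No step bars the case categorically. Hepatitis that meets the DLT definition, leads to a permanent stop and then resolves takes the same path, with exclusion 2(b) the most arguable step.

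**Could such a stop arise?** Section 1.4.1.8 lists Grade 3 autoimmune hepatitis and Grade 2 immune-mediated enterocolitis among the drug-related events that led to discontinuation on the combination in this study, reported only as related to study drug. Section 1.8 names hepatitis and nephrotoxicity when describing nivolumab. An attribution to nivolumab is therefore conceivable. Nothing in the documents shows that one was made.

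**The case against.** The best reply is that the gap needs an attribution the protocol never makes. Causality is recorded against both antibodies together, and an event related to both is already barred. A natural reading for a combination subject is that any drug-related stop counts. This stands as a limit: only an event judged related to nivolumab and not to relatlimab escapes. It does not remove the point, because criterion 2 itself asks for the single-antibody judgment.

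A second reply is that discretion is deliberate. For AST or ALT elevations meeting the DLT definition, Section 4.3.5 already lets the Investigator and Medical Monitor discuss continuing. A categorical bar on re-challenge might seem inconsistent with that. It is not, because a subject who continued under that provision was never permanently stopped.

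A third reply is that relatlimab is the one drug in every re-challenge regimen, so naming it is coherent, and that relatlimab alone is already offered. Both statements are true. But nothing requires relatlimab alone after a nivolumab-attributed stop.

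A reader might also infer more than the documents support:

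- *That these events are nivolumab's doing.* The Grade 3 to 4 drug-related events listed for relatlimab monotherapy in Section 1.4.1.5, and the Grade 3 events listed for it in Section 1.5.1, include no colitis or hepatitis. Monotherapy exposure is redacted, so their absence says nothing about causation.
- *That re-challenge after a nivolumab-related stop is unrestricted.* It is not, given the exclusions and judgments set out above.
- *That the primary efficacy result is at risk.* Section 3.1.5 sends re-challenge responses to a separate analysis.

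**Conclusion.** The point holds, as a minor patient-safety matter of wording. Criterion 2 is narrower than the stopping rule it follows, and no other rule categorically closes the difference for a resolved, non-life-threatening event attributed to nivolumab alone.

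The remaining risk is small. The subject must also progress in follow-up, not be thought at hazard under exclusion 2(f), not be caught by 2(b), and be approved by both the Investigator and the Medical Monitor. How many subjects this could reach cannot be estimated, because the counts are redacted. The primary ORR is unaffected.

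The conclusion rests on two readings. The first is that the closing paragraph of Section 4.3.5 prevails over the Section 4.3.3 sentence where they conflict. The second is that exclusion 2(b) does not clearly reach a resolved drug-induced event.

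**What to change.** In Section 3.1.5 and the matching synopsis paragraph, replace *relatlimab related adverse events* with *study drug-related (relatlimab and/or nivolumab) adverse events* as the condition for combination re-challenge. This matches the causality that Section 6 records. If an option is wanted after a stop attributed only to nivolumab, state that at most relatlimab alone may be given; that regimen is already permitted. Add that the case-by-case paragraph closing Section 4.3.5 does not override this condition.

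The cost is one phrase in two places and a clarifying sentence or two. The downside is that a few subjects lose access to combination re-challenge, which the relatlimab-alone option limits.
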